5.2.1 Inclusion Criteria

- Male or female, aged 21-60 years.
- A BMI categorized as overweight (≥ 25) but not stage II obesity (≤ 35)
- Daily steps < 5,000.

- Ownership of a smartphone device with either the Apple Health or Google Fit application.
- Willingness to carry their phone in their pocket or on their person at all times to track steps during study.
- Willing to download the Pro2col application and connect it with either the Apple Health or Google Fit application.
- Willingness to complete physical tasks including a timed one-mile walk/run, regular or modified push-ups to exhaustion, and chair get-ups to exhaustion.
- For the experimental group, subjects must be willing to follow the application protocol which is laid out later in this document.
- Able to read, understand, sign and date the informed consent document (English only)
- Able and willing to comply with the scheduled visit(s) and study requirements.

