6. CONDITIONS

6.1. Study Administration

All study activities will be performed under the supervision of the investigator in accordance with the protocol requirements, and with adherence to Good Clinical Practices (GCP) and International Conference on Harmonization (ICH E6 R2).

Only study subjects who signed the informed consent form and meet all entry criteria will be enrolled and randomly assigned to a study group.

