7.1. SCREENING

Subjects who signed the informed consent form will have the following assessments performed:

- Inclusion and exclusion criteria
- Medical and medication history
- Demographic and baseline characteristics

Subjects who meet all required entry criteria will be enrolled in the study and will be assigned a subject No./ID in the 100 series starting with "101" and continuing in sequential order until enrollment is met.

Enrolled subjects will be scheduled for a remote consultation with a member of the study staff to go over the details of the study, their condition assignment, and all related materials and procedures for the study.

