7.2. BASELINE TESTING

Subjects who continue to be eligible for this study will then complete baseline testing. Subjective questionnaires will be provided to assess items such as current activity levels, nutrition habits, and lifestyle factors related to health and wellness. Enrolled and randomized subjects will also receive a blood pressure cuff and digital scale to record blood pressure and bodyweight/body composition, respectively. Moreover, subjects will complete electronic calculations to estimate their healthspan and biological age. Finally, subjects will perform three physical fitness tests, including:

- Timed one mile walk/run
- Push-ups (or modified push-ups for women) to exhaustion
- Chair get-ups to exhaustion

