7.3. INTERVENTION

Subjects will follow their assigned condition for 6 weeks. Subjects in the control group will be monitored by study staff but otherwise uninstructed in regard to activity and nutrition. Their adherence to the provided educational materials is entirely up to them. The experimental group will be initiated into a 4-6-week (28-42 days depending on subject availability for the last testing day) progressive protocol on the Pro2col app. They will receive daily updates, notification, and education regarding healthy habits such as exercise, hydration, and improved nutrition practices. An AI coach will be responsible for providing instructions and feedback to all application users.

7.4. **POST-TESTING**

Subjects who complete the 4-6-week (28-42 days depending on subject availability for last testing day) intervention and continue to be eligible for this study will then complete post testing. Subjective questionnaires will be provided to assess items such as current activity levels, nutrition habits, and lifestyle factors related to health and wellness. Enrolled and randomized subjects will also receive a blood pressure cuff and digital scale to record blood pressure and bodyweight/body composition, respectively. Moreover, subjects will complete electronic calculations to estimate their healthspan and biological age. Finally, subjects will perform three physical fitness tests, including:

- Timed one mile walk/run
- Push-ups (or modified push-ups for women) to exhaustion
- Chair get-ups to exhaustion

Finally, upon completion of the study (or early withdrawal), subjects will be directed to delete the investigational application from their smart device, and no further data will be collected.

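### An inclusion criterion worded for the experimental group only, with eligibility gates that can fall after assignment is known, could let unwilling subjects be removed from PRO on a ground that does not apply to control

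*Combined protocol and SAP*

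**What the plan says.** - **Arm-specific criterion.** Section 5.2.1 includes "For the experimental group, subjects must be willing to follow the application protocol which is laid out later in this document". The other inclusion criteria are worded for all subjects, including "Able and willing to comply with the scheduled visit(s) and study requirements".
- **No counterpart in control.** Section 7.3 says of control subjects: "Their adherence to the provided educational materials is entirely up to them".
- **Order in 5.1 and 6.1.** Section 5.1 places random assignment after baseline testing and enrolment. Section 6.1 says that only consented subjects who "meet all entry criteria will be enrolled and randomly assigned to a study group".
- **Order in 7.1 and 7.2.** Section 7.1 enrols subjects who meet the entry criteria, then schedules a remote consultation "to go over the details of the study, their condition assignment, and all related materials and procedures for the study". Section 7.2 follows with: "Subjects who continue to be eligible for this study will then complete baseline testing". It also states: "Enrolled and randomized subjects will also receive a blood pressure cuff and digital scale".
- **Later gate.** Section 7.4 makes post-testing conditional on completing the intervention and still being eligible.
- **Status labels.** The classification table in 7.6 counts a consented subject who fails entry criteria, or who withdraws before baseline testing, as a screen failure.
- **Analysis sets.** Section 10.3.1 names no efficacy population. A per protocol population appears only in the abbreviation list, and the safety population in 10.3.3 is not defined.

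**The concern.** Randomisation protects the comparison only if whatever decides who stays in is applied equally to both arms, or before anyone knows the arm. A willingness criterion tied to one arm, combined with an eligibility check after the arm is known, can break that protection. A PRO subject who hears about the fasting, diet and step targets and declines would fail an entry criterion. A control subject with the same attitude has no programme to decline and stays.

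Willingness to change habits is plausibly related to change in steps, body composition, fitness tests and self-reported lifestyle scores, which are among the primary outcomes in 4.1. The trial is unblinded (6.4), so both staff and subjects know the arm. Under 7.6, a subject lost between disclosure and baseline testing could be recorded as a screen failure and so not appear as a post-randomisation loss. The result would be a PRO arm selected for motivation, compared with an unselected control arm.

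**Working it through.** **1. Can the criterion act after assignment?** There are three points at which eligibility is judged.

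| Point | Arm known? | Could the PRO-only criterion act unequally? |
|---|---|---|
| Entry check, by the order in 5.1 and 6.1 | No | No, provided it is asked of everyone; the text does not say so |
| Gate into baseline testing, by the order in 7.1 and 7.2 | Yes | Yes |
| Gate into post-testing, 7.4 | Yes, on any reading | Yes |

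**2. The plan's own sample size.** Inputs: standardised effect 0.8 and total 50 (10.1); significance level 0.05 (10.3.1). Two-sided testing, 80% power and 1:1 allocation are not stated and are assumed.

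n per arm = 2 × (1.960 + 0.842)² / 0.8² = 2 × 7.85 / 0.64 = 24.5, so 25 per arm and 50 in total. The stated figure reproduces (a t-based calculation gives 26 per arm). The present point does not change it.

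**3. Bias from one-sided removal.** Let f be the share of unwilling subjects and δ the amount, in SD, by which their change is worse whichever arm they are in. With no true effect and willing subjects averaging μ:

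- PRO mean after removal = μ
- Control mean = (1 − f) × μ + f × (μ − δ) = μ − fδ
- Bias towards PRO = fδ

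The documents give neither f nor δ. Assumed ranges: f = 5-30%, δ = 0.5-1.0 SD.

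- Low end: 0.05 × 0.5 = 0.025 SD; 0.025 / 0.8 = 3% of the planned effect
- Middle: 0.20 × 0.8 = 0.16 SD; 0.16 / 0.8 = 20%
- High end: 0.30 × 1.0 = 0.30 SD; 0.30 / 0.8 = 38%

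**4. Type I error.** Simulation with no true effect, unwilling subjects removed from PRO only, and a two-sample t test at two-sided 0.05. The arm sizes are those randomised: 25 (the targeted 50) and 100 (the maximum of 200 in 5.1, assuming 1:1).

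| Unwilling f | Gap δ (SD) | Bias (SD) | 25 per arm | 100 per arm |
|---|---|---|---|---|
| 5% | 0.5 | 0.025 | 5.1% | 5-6% |
| 10% | 0.5 | 0.05 | 5.3% | 6.2% |
| 20% | 0.8 | 0.16 | 7.7% | 17% |
| 30% | 1.0 | 0.30 | 14% | 44% |

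Removal also shrinks PRO. From 25 randomised it leaves on average 25 × 0.8 = 20 at f = 20% and 25 × 0.7 = 17.5 at f = 30%, against the minimum target of 20 completers per group in 5.1.

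**5. If the question is asked of everyone before randomisation and all randomised subjects are analysed as assigned**, this bias is zero and the type I error from this source stays at 5%.

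**The case against.** The strongest reply is that 5.1, 6.1 and the first part of 7.1 all have subjects meet the entry criteria before assignment is known. The criterion sits in the entry list, so it can be read as a conditional question put to everyone at screening: would you follow the programme if assigned to it? No passage tells staff to reassess willingness after disclosure, and the only check the documents specifically place at baseline, the PHQ-9 cut-off, applies to both arms. All of this is fair. The text does not, however, say that the question is put to everyone; 7.1 and 7.2 give an order that conflicts with 5.1; and the 7.4 gate falls after assignment whichever order is used.

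A reader might infer that unwilling subjects will be removed from PRO and cannot be removed from control. The documents support neither half. They permit the removal without prescribing it. Control subjects can be lost through the general compliance criterion, the PHQ-9 exclusion, investigator discretion or their own withdrawal. Only this one criterion is asymmetric.

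A reader might also treat the worst case as a plain 0.3 SD shift with full arms, which gives false-positive rates of 18% at 25 per arm and 56% at 100. That overstates it. The mechanism itself reduces PRO and leaves extra spread in control, and simulating it gives about 14% and 44%.

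Finally, this is an open-label pilot with an exploratory objective, and some refusers would be lost to withdrawal whatever the criterion says. That stands: rewording alone removes only part of the imbalance, so follow-up and the analysis set have to be addressed too.

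**Conclusion.** The point holds as a risk that the wording creates, not as a demonstrated exclusion. One inclusion criterion applies to PRO alone, the sections disagree on whether assignment precedes baseline testing, an eligibility gate at post-testing comes after assignment on any reading, and no efficacy population restores removed subjects. Any resulting bias would run towards the app, given that unwilling subjects do worse in either arm.

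Its size cannot be fixed from the documents. Over the assumed ranges it runs from negligible to 0.30 SD, and for a given bias the false-positive risk grows with enrolment. The upper figures need both a 30% unwilling share and a full 1 SD gap. The correction is worth making before enrolment because it takes only a few sentences and leaves the sample size of 50 unchanged.

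**What to change.** 1. In 5.2.1, replace the arm-specific criterion with: *Willing to follow either the application protocol or the control condition, as assigned*. Ask it of every subject before randomisation.
2. Reconcile 5.1, 6.1, 7.1 and 7.2 so that baseline testing and all eligibility checks come before randomisation and before the assignment is disclosed.
3. State in 7.2 and 7.4 that failing or refusing the assigned programme is not in itself a ground for ineligibility, and that such subjects are still asked to complete post-testing. Withdrawal on safety grounds under 7.5 is unaffected.
4. In 10.3.1, state that all randomised subjects are analysed in their randomised arm. Make clear in 7.6 that a subject lost after randomisation is not counted as a screen failure.

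Cost: a few sentences. A few subjects may decline at screening, and keeping refusers in the analysis may slightly dilute the estimated effect.

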5.2.2 Exclusion Criteria

Subjects presenting any of the following will not be included in the study:

- Currently taking (within the past 30 days) ergogenic dietary supplements including, creatine, protein, amino acids, or stimulants other than caffeine (yohimbe, ephedrine, etc.)
- Currently taking performance enhancing drugs (testosterone or other anabolic-androgenic steroids), human growth hormone, insulin, etc.
- History or current malignancy
- Receiving chemotherapy agents or radiation treatments
- Musculoskeletal disease (muscular dystrophy, arthritis, etc.)
- Recent (<3-months) musculoskeletal injuries
- BMI < 25 or > 35 kg/m²
- Diagnosis of a terminal illness
- Use of prescription medications that influence body composition (i.e., prescription hormone therapies, etc.)
- History of alcohol abuse
- History or current drug abuse
- History or current diagnosis of depression.
- History or current diagnosis of suicidal thoughts/ideation.
- A score of \geq 10 arbitrary units on the PHQ-9 during baseline testing.
- History or current cigarette smoke (including vaping) within the past 14 days from the screening visit
- Insulin-dependent diabetes and/or metformin use
- Chronic kidney or liver disease
- Has significant concurrent illnesses (controlled or uncontrolled), such as diabetes, lupus, epilepsy, or cardiac disorders, hepatitis B/C, HIV, serious mental health illness such as dementia or schizophrenia; psychiatric hospitalization in the past two years,

or other, which in the opinion of the investigator, such conditions might be aggravated as a result of treatment

- The investigator feels that for any reason the subject is not eligible to participate in the study
- History of uncontrolled cardiovascular disease (i.e., myocardial infarction, hypertension, hypercholesterolemia, peripheral vascular disease, other)
- Developmental disability or cognitive impairment that would preclude adequate comprehension of the informed consent form and/or ability to follow study subject requirement and/or record the necessary study measurements
- A family member of the investigator or an employee of the investigator
- Participation in any other investigational study within 30 days prior to consent.

6. CONDITIONS

6.1. Study Administration

All study activities will be performed under the supervision of the investigator in accordance with the protocol requirements, and with adherence to Good Clinical Practices (GCP) and International Conference on Harmonization (ICH E6 R2).

Only study subjects who signed the informed consent form and meet all entry criteria will be enrolled and randomly assigned to a study group.

6.2. Identity of Experimental Condition

The Experimental Condition involves the use of a novel smartphone application. This application provides a digital diagnostic score to calculate healthspan and biological age, along with AI and group community-based coaching dynamics. Subjects will be assigned a 4-6-week (28-42 days depending on subject availability for last testing day) progressive protocol designed to implement lifestyle changes and solidify adherable practices including the following:

- Daily practice of intermittent fasting, eating within a time restricted eating window ranging from 8 to 12 hours.
- Increased daily steps.
- Increased awareness of hydration practices.
- Journaling
- Adherence to a lower carbohydrate, higher-protein diet.
- Improved exercise habits.
- Stress management
- Sleep habits
- Improved lifestyle risk factors, like smoking and alcohol intake

The above factors are individualized based on subject responses to questionnaires within the application. An AI-based coach and application algorithms will then send users push notifications to improve adherence to their new lifestyle factors as well as provide feedback for their logged data entries. Specifically, the application users will be required to connect the Pro2col application with either the Apple Health or Google Fit application so that necessary data can be transmitted between these applications without user input. The application creates a personalized protocol by using responses from the embedded health questionnaire to establish baseline figures that the user will improve upon. For example, if a user reports walking between 4,001-5,000 steps daily, their program will start them at 4,000 steps in week 1, gradually increasing each week until they reach the program's goal (e.g., 10,000 steps). Below are the key elements used to generate an individualized protocol, with specific goals for this user:

Steps Goal: 10,000 Steps

Incremental Approach: Starting from the user's baseline, steps will gradually increase each week to reach the target of 10,000 steps over a 4-6-week period (28-42 days depending on subject availability for the last testing day).

Example:

Week 1: Starting at the baseline (e.g., 4,000 steps)

Week 2: 5,200 steps

Week 3: 6,400 steps

Week 4: 7,600 steps

Week 5: 8,800 steps

Week 6: 10,000 steps

Calorie Goal: Moderate Fat Loss

Caloric intake will be reduced on average by 250 calories from basal calorie needs.

Hydration Goal: Subjects will have a target water consumption goal of 10 Cups of Water

Incremental Approach: Starting from the user's baseline (e.g., 5 cups), water intake will increase each week until reaching 10 cups over 6 weeks.

Example:

Week 1: 5 cups Week 2: 6 cups Week 3: 7 cups Week 4: 8 cups Week 5: 9 cups Week 6: 10 cups

Eating Window: 8 Hours

Incremental Approach: The eating window will decrease each week until it reaches an 8-hour window over 6 weeks. For example if they are currently eating 16 hours per day (for example 6 am to 10 pm), we would modify as such:

Example:

Week 1: 16-hour eating window

Week 2: 14-hour eating window

Week 3: 12-hour eating window

Week 4: 10-hour eating window

Week 5: 9-hour eating window

Week 6: 8-hour eating window

Subjects will also be awarded with points within the application for hitting their goal.

6.3. Identity of Control Condition

Subjects randomly enrolled in the control group will be given materials published by the American Heart Association (AHA) and United States Department of Agriculture (USDA). The AHA flyer is linked here and the USDA booklet is linked here.

6.4. Blinding

Study officials nor participants will be blinded to study conditions.

6.5. Expected / Unexpected Risk

Risks or side effects associated with physical fitness programs:

- Musculoskeletal injury
- Fatigue
- Shortness of Breath
- Light-headedness or Dizziness
- Fainting

Risks or side effects associated with intermittent fasting:

- Fainting
- Dizziness
- Hunger

Risks or side effects associated with low carbohydrate diets:

- Fainting
- Dizziness
- Hunger
- Fatigue

General Statement:

Although no immediate risks or side effects are anticipated for this study, all aspects of this clinical investigation will be conducted under the direct supervision and oversight of the investigator and designated study staff. Adverse events whether spontaneous, or self-reported, will be collected and analyzed.

6.6. Prior and Concomitant Medications and Therapies

Subjects must abstain from exclusionary procedures/medications/therapies as listed under the Exclusion Criteria for the duration of the study, and prior to the study relative to certain Exclusion Criteria.

7. STUDY PROCEDURES

Study procedures as described in this section are depicted in the schedule of study visits of Appendix 1. Methodologies for study outcomes are described in Appendix 1.

7.1. SCREENING

Subjects who signed the informed consent form will have the following assessments performed:

- Inclusion and exclusion criteria
- Medical and medication history
- Demographic and baseline characteristics

Subjects who meet all required entry criteria will be enrolled in the study and will be assigned a subject No./ID in the 100 series starting with "101" and continuing in sequential order until enrollment is met.

Enrolled subjects will be scheduled for a remote consultation with a member of the study staff to go over the details of the study, their condition assignment, and all related materials and procedures for the study.

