5. INVESTIGATIONAL PLAN

5.1. Overall Study Design and Plan

This is a non-blinded randomized controlled pilot trial conducted over up to 8 weeks. Week 0 will involve baseline measurements and enrollment, Weeks 1-6 constitute the intervention, and Week 7 to 8 is reserved for post-testing. The study will enroll up to 200 participants, with a minimum of 50 participants who meet the inclusion criteria, and a minimum target of 20 participants completing the study in each group (experimental and control).

Participants will be recruited from across the United States using a decentralized electronic database. The study will include individuals aged 21-60 with a BMI \geq 25 (overweight) and \leq 35. Additionally, qualified subjects must have current daily activity records that show an average daily step count under 5,000. Participants must also be free of disease and must own either a personal smartphone device with the Apple Health or Google Fit application. Finally, participants must be willing to keep their device with them at all times to ensure accurate activity tracking.

Following baseline testing and enrollment in the study, participants will be randomly assigned to either the control (CON) or experimental (PRO) group. The control group will receive subject-facing materials depicting current general activity recommendations as published by the American Heart Association (AHA) and current dietary guidelines provided by the United States Department of Agriculture (USDA). The experimental group will be enrolled in the Prime Health Technologies software (Pro2col), which provides a digital diagnostic score to calculate healthspan and biological age, along with AI and group community-based coaching dynamics. Subjects will be assigned a 6 week progressive protocol targeting improvements in daily activity levels, nutritional awareness, and overall lifestyle risk factors. Both groups will then be monitored by study staff throughout the duration of the intervention period with post-testing taking place following the last week of the experiment.

Due to the remote nature of subject recruitment, no in-person facility visits are required for participants.

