Symptoms of depression will be assessed using the Patient Health Questionnaire-9 (PHQ-9). This questionnaire is a previously validated tool that collects information about depression symptoms in users. The user answers nine questions relating to depression symptoms on a scale of 0-3, with 0 representing no issues at all, and 3 representing experiencing the symptom nearly every day. The user's total score is a summation of their responses, and is scored as follows:

1-4 Minimal depression5-9 Mild depression10-14 Moderate depression15-19 Moderately severe depression20-27 Severe depression

Importantly, users who score ≥ 10 arbitrary units on the PHQ-9 during baseline testing will fail to continue being eligible for the study. In this instance, a study staff member will contact the individual, explain the reasoning, and thank the subject for their time. Due to the remote nature of this study, it is impossible to partner with a mental health clinic for subject referrals. Subjects will be encouraged to speak with their primary care physician if they are

concerned about their score. An email script will be crafted to provide further information for this instance.

Quality of Life

Quality of life will be assessed by the previously validated 36-item Short Form survey (SF-36). The SF-36 houses a number of questions pertaining to various factors of quality of life. Subjects will answer questions in a variety of manners, from simple "yes" or "no" responses to Likert-adjacent scaled responses that allow the subject to select the answer that best corresponds to their attitudes and beliefs. The scoring instructions for the SF-36 can be accessed in the .pdf linked here.

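### Section 7 can be read as disclosing the arm before baseline testing, which is inconsistent with the order in Section 5.1

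*Combined protocol and SAP*

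**What the plan says.** Section 5.1 gives the order directly: "Following baseline testing and enrollment in the study, participants will be randomly assigned to either the control (CON) or experimental (PRO) group". Section 6.1 limits randomisation to consented subjects who "meet all entry criteria will be enrolled and randomly assigned to a study group". One entry criterion is settled late. Section 5.2.2 excludes subjects who score 10 or more "arbitrary units on the PHQ-9 during baseline testing", and the Depression entry in Appendix 1 repeats that "users who score ≥ 10 arbitrary units on the PHQ-9 during baseline testing will fail to continue being eligible for the study".

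Section 7 is arranged differently. Section 7.1 (Screening) enrols subjects, numbers them and schedules them for "a remote consultation with a member of the study staff to go over the details of the study, their condition assignment". Section 7.2 then opens: "Subjects who continue to be eligible for this study will then complete baseline testing". The same section says that the blood pressure cuff and scale used for the baseline readings go to subjects it describes as already enrolled and randomised.

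Three other points bear on this. Section 6.4 states that neither staff nor participants are blinded. Section 10.3.1 analyses changes and names no baseline-adjusted model. Section 7 refers to a timetable: "Study procedures as described in this section are depicted in the schedule of study visits of Appendix 1". That schedule is not in the text available for this review.

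**The concern.** Staff are likely to work from Section 7. Read in sequence, it has the subject hear the arm assignment and then do the baseline tests.

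Several primary outcomes depend on effort or self-report: push-ups and chair get-ups to exhaustion, a mile at the subject's own pace, and the questionnaire-based scores, including healthspan and biological age. A subject who knows the arm may try harder or less hard, or answer differently. Because the analysis uses change from baseline, a baseline difference created this way passes straight into the between-group comparison. It could favour either arm. Phone-recorded steps, cuff blood pressure and scale-measured body composition are less exposed.

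The PHQ-9 adds a second problem. If assignment comes before baseline testing, subjects excluded on that score leave after assignment. Section 6.1 does not allow this, and Section 10 has no rule for handling it.

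**Working it through.** **Step 1. Set the passages side by side.**

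| Place | What it implies about order | Strength |
|---|---|---|
| 5.1 | Baseline testing, then randomisation | Explicit |
| 6.1 with 5.2.2 and Appendix 1 (Depression) | PHQ-9 before randomisation | Explicit, for the PHQ-9 only |
| 7.1 | Consultation on the assignment listed under Screening | Inferred; no date given |
| 7.2, opening sentence | Baseline testing follows the 7.1 steps | Inferred from sequence |
| 7.2, device sentence | Recipients already randomised | Weak; 7.4 repeats the sentence at post-test, where it says nothing about order |

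Appendix 1 also says that the cuff and scale are delivered on enrolment, which weakens the device cue further. Section 7 contains no randomisation step. The contrary order is therefore a reading of Section 7, not a statement in it. But an assignment cannot be discussed before it exists, and the discussion is listed ahead of a section that begins with baseline testing as the next step.

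**Step 2. Sample sizes for the illustration.** Section 10.1 gives 50 participants for an effect size of 0.8. Assuming a two-sided 5% test, 80% power and 1:1 allocation (none of these three is stated in full), the normal approximation gives n per arm = 2 × (1.960 + 0.842)² / 0.8² = 24.5, rounded up to 25, or 50 in total. This matches the plan. Section 5.1 also gives a minimum target of 20 completers per group and a cap of 200 participants. With 1:1 allocation and no dropout, the cap is 100 per arm.

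**Step 3. Effect of an assumed baseline shift.** Change is post-test minus baseline. If knowing the arm moves one arm's baseline mean by b (in SD of change) and post-test values are unaffected, the difference in mean change moves by b in the opposite direction. With no true effect, a two-sided two-sample t test at 5% rejects with the probability given by a noncentral t distribution with 2n − 2 degrees of freedom and noncentrality b × √(n/2).

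Example: for n = 20 and b = 0.2, the noncentrality is 0.2 × √10 = 0.632 on 38 degrees of freedom. The critical value is 2.024 and the rejection probability is 9.5%.

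| Per arm | b = 0.1 | b = 0.2 | b = 0.3 | b = 0.5 |
|---|---|---|---|---|
| 20 | 6.1% | 9.5% | 15.2% | 33.8% |
| 25 | 6.4% | 10.7% | 18.0% | 41.0% |
| 100 | 10.8% | 29.1% | 56.0% | 94.0% |

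Every value of b is an assumption, since the documents give no basis for any of them. The two-sample test is used because the two arms are independent groups; Section 10.3.1 names paired t tests. PHQ-9 removals after assignment are not quantified, because the documents give no rate.

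**The case against.** The strongest reply is that Section 5.1 is the only explicit statement of when randomisation occurs, and it already has the order this review would want. Section 7.1 says only that the consultation will be scheduled, so it could take place after baseline testing. The device sentence looks like repeated template text, and the visit schedule may show the right order. All of this stands, so the bias is a possibility and not a finding. It does not remove the inconsistency: no passage says which section prevails, and even a clear schedule would leave Section 7 worded against Section 5.1.

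A further reply is that Section 7.1 enrols only subjects who meet all entry criteria, so on its literal terms they have already passed the PHQ-9. That is fair, but the PHQ-9 is scored at baseline testing, which Section 7.2 places later. Section 7 is thus unclear on this point too.

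A reader might infer more than the text supports in two places:

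- **That the entry criteria require all baseline tests to precede randomisation.** They require this only of the PHQ-9. The order for the fitness tests rests on Section 5.1 alone.
- **That the app-based baselines are collected only after assignment, or only in the experimental arm**, because Section 5.1 enrols that arm in the software after assignment. Section 4.1 lists these scores at week 0 without limiting them to one arm. Section 7.2 includes the healthspan and biological age calculations in baseline testing for subjects generally. Section 5.2.1 requires every subject to be willing to download the app. Enrolment in the software can mean the start of the coaching programme.

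**Conclusion.** The point holds as an inconsistency of wording with a conditional consequence. Section 7 can be read as disclosing the arm before baseline testing, whereas Section 5.1 randomises afterwards. The balance of the text favours Section 5.1, but the order staff would follow is uncertain. If all baseline measures are completed before assignment, the bias does not arise.

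A reader might conclude that the plan does randomise before baseline, or that the trial's false-positive rate is inflated by the amounts tabulated. The documents support neither. Section 7 states no randomisation step, and the rates follow from assumed shifts. At 0.1 SD with 20 to 25 per arm the inflation is negligible (6.1% to 6.4% against 5%). The largest figures combine a large assumed shift with the enrolment cap, although Section 10.1 targets 50 participants. What the table does show is that a fixed shift matters more as enrolment grows.

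Correction is still worthwhile, because a baseline taken with the arm known cannot be repaired afterwards.

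**What to change.** Align Sections 7.1 and 7.2 with Section 5.1: all baseline measures including the PHQ-9 completed and recorded, then randomisation, then disclosure of the assignment.

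- In 7.1, take the discussion of the assignment out of the screening consultation and put it in a step after 7.2.
- In 7.2, describe those who receive the cuff and scale as eligible subjects, not as randomised ones.
- In 7.2, state that the app-based week 0 scores are completed before assignment in all subjects, and that coaching features start after assignment, in the experimental arm only. Section 7.3 has the AI coach giving feedback to all application users, so without this statement control subjects could be exposed to it through their baseline use of the app.
- Make the visit schedule cited in Section 7 show the same order.

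The PHQ-9 exclusion text and the status classification tables need no change for this purpose.

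The cost is amendment wording and a reordering of remote steps. Some cuffs and scales will go to people who are never randomised. If enrolment is under way, the change protects only subjects not yet tested. Open-label bias at post-test remains whatever the order.
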